## **9.5 INTERIM ANALYSES**

An interim analysis will be conducted by the DMC as outlined in the CTP. If based on the interim analysis it is decided to stop the trial for overwhelming efficacy, this analysis used by the DMC will be considered the primary analysis for the primary endpoint. This analysis will be repeated using the data of the final database lock. All other analyses including analyses of the key secondary endpoints will be conducted on the final database lock to provide most complete available data.

Only events that occurred up to one day prior the predefined interim analysis cut-off date will be considered for the analysis of the primary endpoint as well as CV death at interim. Patients without events up to this time will be censored at the predefined interim analysis cut-off date.

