7.3.1 Primary endpoint analyses

The primary endpoint will be analysed using a Cox proportional hazards model with age (continuous), gender, treatment, geographical region, baseline status of diabetes (DM, pre-DM, no DM), baseline LVEF ($\leq 30\%$, $>30\%$ to $\leq 35\%$, $> 35\%$) and eGFR (CKD-EPI)_{cr} at baseline (continuous) as covariates.

The time to the event of interest will be calculated by (event date – randomisation date) + 1. All events observed after randomisation until completion of the planned treatment phase will be included in the analysis. Patients who do not have an event during the trial period will be censored at the individual end of the planned treatment phase or the last day that the patient was known to be free of the event, whichever is earlier. Time to censoring will be calculated by (individual end of the planned treatment phase or the last day known to be free of the event – randomisation date) + 1. For patients who have more than one primary endpoint event during the trial, the time to the first occurrence of the primary endpoint event will be considered for the primary analysis. Only the adjudicated and confirmed events are included in the primary analysis.

To detect any heterogeneity in the treatment effect among diabetic patients, pre-diabetic patients and non-diabetic patients, a subgroup analysis will be performed by including diabetic status by treatment interaction term into the Cox model.

Standard subgroup analyses of the primary endpoint include geographical region, sex, BMI, renal function, prognostic factors, age, ethnicity, race and different background therapies etc. More details will be specified in the TSAP.

A sensitivity analysis will be provided based on the treated set but only including any events up to 30 days after treatment discontinuation.

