7.4 INTERIM ANALYSES

The safety and conduct of the trial will be monitored by an independent DMC. Details on this process are outlined in the DMC charter.

There will be one unblinded interim analysis to be conducted by the DMC. At the time of the interim analysis, the ExSC, SEC, Sponsor, CRO and all trial/site personnel will stay blinded to the interim results. For blinding, please also refer to [Section 4.1.5.1](#).

After approximately 500 primary adjudicated outcome events have been accrued (approximately 60% of information is available) an interim analysis will be performed.

The following Hwang, Shih and De Cani α -spending function for the analysis at information fraction t_k (planned to be approximately 60%) with parameter $\gamma = -8$ will be used:

$$\alpha^*(\gamma, t_k) = \min \left\{ \alpha, \quad \alpha \frac{1 - e^{-\gamma t_k}}{1 - e^{-\gamma}} \right\} = \min \left\{ 0.025, \quad 0.025 \frac{1 - e^{8t_k}}{1 - e^8} \right\}$$

The chosen alpha-spending function spends an alpha-level of 0.001 at the time of approximately 60% of information for the interim analysis.

If the p-value for the primary endpoint and the p-value for CV-death (from the primary Cox proportional hazards model) are lower than the cut-off to be evaluated from the alpha spending function (planned at 0.001 one-sided), the trial will be stopped for overwhelming efficacy. In this case, the hierarchy will be tested as specified in [Section 7.2](#). Otherwise the trial will be continued.

The final alpha level is therefore planned at a one-sided alpha-level of 0.0248 which translates in a two-sided alpha of 0.0496.

The event rate will be assessed by the trial team in a blinded manner only during trial recruitment and before the unblinded interim analysis (see [Section 7.7](#)).

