### **6.8.3 Censoring**

The underlying principle is that the censoring date should be the last date a patient was known to be free of an endpoint event (e.g. free of each component of HHF + CV death).

For all endpoints except all-cause mortality and cause-specific death, patients without occurrence of a specific endpoint (composite endpoint or individual components) will be considered censored at the individual day of trial completion.

The individual day of trial completion will be the latest of:

- the last date the patient could be followed up for all non-fatal events as documented in the eCRF
- last onset of an AE or date of death
- onset dates of adjudicated events
- end of treatment
- last visit date (NYHA class, EQ-5D, KCCQ, pregnancy test, vital signs, ECG, or central laboratory- reported )

Censoring is considered independent from study drug intake.

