#### Endpoints of any cause-specific death, e.g. CV death

The same censoring rule as in all-cause mortality applies, and in addition, date of death if died from other causes than the one specified in the endpoint.

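### Does the interim censoring rule in SAP 9.5 keep earlier non-CV deaths, withdrawals and losses at risk until the cut-off?

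*SAP*

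**What the plan says.** SAP section 9.5 limits the interim analysis to events up to the day before a predefined cut-off. Those events "will be considered for the analysis of the primary endpoint as well as CV death at interim". It then states: "Patients without events up to this time will be censored at the predefined interim analysis cut-off date". If the trial stops for efficacy, "this analysis used by the DMC will be considered the primary analysis for the primary endpoint", and "This analysis will be repeated using the data of the final database lock".

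Protocol section 7.4 requires two results to cross the boundary before the trial stops. The condition begins "If the p-value for the primary endpoint and the p-value for CV-death", and the p-values come from the primary Cox model. Protocol section 7.3.1 censors that model at the end of the planned treatment phase or "the last day that the patient was known to be free of the event, whichever is earlier".

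SAP section 6.8.3 gives the general rule: "The underlying principle is that the censoring date should be the last date a patient was known to be free of an endpoint event". For cause-specific death it adds censoring at "date of death if died from other causes than the one specified in the endpoint". For a composite endpoint it takes the earliest censoring date among the components.

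**The concern.** The sentence in 9.5 names a single censoring date and does not mention anyone whose follow-up ended sooner. Taken literally, a patient who died of a non-CV cause a year before the cut-off would still count as at risk of HHF and CV death for that year. The same holds for patients who withdrew or were lost.

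For non-CV death this gives a subdistribution-type hazard ratio, which SAP section 7.4.2 plans only as a sensitivity analysis (Fine-Gray). For withdrawal and loss it credits event-free time that nobody observed. If exits differ between arms, the hazard ratio is pulled in one direction: towards 1 if placebo has more of them, away from 1 if empagliflozin does.

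The rule covers both tests needed to stop the trial, and its primary-endpoint result would stand as the primary analysis after an early stop. The repeat on the final database lock would not replace it.

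**Working it through.** **Reading the passages together**

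1. SAP 9.5 opens by saying that the interim is conducted as the protocol sets out.
2. Protocol 7.4 takes the interim p-values from the primary Cox model.
3. Protocol 7.3.1 censors that model at the earlier of two dates, one of them the last day known event-free.
4. SAP 7.4.1 describes one primary model and one spending function for the interim and the final analysis.
5. SAP 6.8.3 sets the censoring rules for the endpoints in sections 7.4 to 7.6. Nothing in 9.5 says it overrides them.
6. The COVID-19 analyses in SAP 7.4.2 and 7.5.1.1 give calendar cut-offs as censoring dates in the same shorthand, also without adding that earlier dates still apply. Those are plainly data cuts.

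**The plan's own figures**

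- Required events (SAP 9.6: HR 0.80, two-sided 0.05, 90% power): 4 × (1.960 + 1.282)² / (ln 0.80)² = 844.1, so 845, against the stated 841.
- Interim level (gamma = −8, 60% information): 0.025 × (1 − e^4.8) / (1 − e^8) = 0.00101, against the stated 0.001.

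Neither depends on the censoring sentence.

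**Effect if 9.5 were followed literally**

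This was checked by simulation, with these inputs:

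- From the documents: 15% yearly placebo event rate, used as a hazard of −ln 0.85 = 0.1625; HR 0.80; 18-month accrual; 3600 or 2850 patients; cut-off at event 500; drop-out planned below 1% per year.
- Assumed: non-CV death of 1 to 3% per year; loss of 0.5 to 1% per year; CV death at 0.06 per year before HHF and three times that after.

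Each simulated trial was fitted twice with an unadjusted Cox model. The first fit censored at the earliest of cut-off, non-CV death and loss. The second censored every event-free patient at the cut-off.

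| Non-CV death and loss per year | Shift in primary HR, N 3600 / 2850 |
|---|---|
| Equal in both arms (1% and 0.5%, or 3% and 1%) | 0.0005 or less |
| Death 3% placebo, 2% empagliflozin; loss 0.5% both | +0.0052 / +0.0065 |
| Same, reversed | −0.0047 / −0.0056 |
| Death as in row 2; loss 1% placebo, 0.5% empagliflozin | +0.0077 / +0.0095 |
| Same, reversed | −0.0072 / −0.0087 |

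In the equal-exit cases 51 to 137 patients are carried past their exit, adding 1.0 to 3.2% to person-time. The CV-death hazard ratio shifts by nearly the same amounts.

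Scale: the standard error of the log hazard ratio at 500 events is √(4/500) = 0.0894. The largest shift in the table is ln(0.8095/0.80) = 0.0118, and 0.0118 / 0.0894 = 0.13 standard errors.

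A separate run used harsher inputs: placebo hazard 0.15, non-CV death 4% per year on placebo and 1.5 times that on empagliflozin, loss 1%, N 2850. The hazard ratio went from 0.7939 to 0.7812, which is |ln(0.7812/0.7939)| / 0.0894 = 0.18 standard errors.

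**Stopping rule**

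Both p-values must be below about 0.001 one-sided. Under the null, the joint crossing probability is about 0.0001. The literal rule moves it to between 0.00007 and 0.00016, and it stays below 0.0004 for correlations of 0.4 to 0.8 between the two test statistics. At HR 0.80 the joint stopping probability is about 6 to 7% and moves by 0.7 to 1.5 percentage points.

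**The obvious repair is not neutral**

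Capping at the earlier of the cut-off and the 6.8.3 date would also affect patients still in the trial. Their 6.8.3 date at an interim is taken here to be the last documented contact. On-site visits are up to 24 weeks apart, with telephone calls 10 to 12 weeks after each. Simulated with equal exits, that wording removes 14 to 18% of person-time if on-site visits set the date, or 7 to 9% if calls count, and moves the hazard ratio by up to 0.007. In the same setting the literal 9.5 wording adds 1.6 to 1.9% of person-time and moves it by 0.0003 or less.

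**The case for a change.** The strongest case for a change is that 9.5 is the specific rule for the interim, and a specific rule can be read as replacing a general one. Where the SAP truncates follow-up at a fixed number of days after treatment stop, section 6.8.3 does write out the minimum of two dates; 9.5 does not. Protocol 7.3.1 does not name non-CV death. The unblinded results are prepared by an independent team outside the conduct of the trial (protocol 4.1.5.1), so unwritten intent is a weaker safeguard there.

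It stands that the clause is missing and that 9.5 has no pointer to 6.8.3. It is also true that a large excess of non-CV death on empagliflozin would make the literal rule flatter the drug. In the harsher setting (placebo 4% per year, 1.5 times that on empagliflozin), the chance of crossing on the primary endpoint alone at HR 0.80 rose from 0.29 to 0.3475. Under the null, crossings went from 0.002 to 0.003 of 3000 trials, that is from six to nine. The documents give no reason to expect such an excess, and the stopping rule also requires CV death to cross.

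The argument from specificity is weak. It needs a programmer to keep patients recorded as dead at risk of CV death, against the explicit rule for cause-specific death in 6.8.3.

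**Conclusion.** This is a clause left unsaid that analysts would fill in the ordinary way: stop time at risk at non-CV death, withdrawal or loss, and cut everyone else at the interim date. The protocol sections that 9.5 relies on, and SAP 6.8.3, already lead there.

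If the sentence were followed to the letter, the interim result would remain sound. The shift is 0.0005 or less with balanced exits and up to about 0.010 under the tabulated imbalances, or about 0.013 in the harsher case. All are below 0.2 of a standard error. Type I error of the joint rule is not materially affected, and 841 events, the 0.001 and 0.0248 levels and the stated power do not change.

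The sizes rest on assumed rates of non-CV death and loss, an assumed CV-death hazard and unadjusted models. The reading of 9.5 as a data cut rests on none of these. No change to the plan follows.

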## **9.6 DETERMINATION OF SAMPLE SIZE**

The trial is designed to achieve a power of 90% for a two-sided test with  $\alpha=0.05$  and hazard ratio 0.80. To achieve this at least 841 patients with a primary event are required.

Including the interim analysis with Hwang, Shih and De Cani  $\alpha$ -spending function at 60% information with parameter  $\gamma = -8$  will diminish the power only slightly to 89.98%.

The drop-out rate from the trial is assumed to be very low (<1% per year) and is not considered for determination of sample size.

A 15% yearly event rate in the placebo group is assumed. Assuming an accrual period of 18 months and a follow-up period of 20 months, it was planned to randomise 2850 patients to accrue 841 events.

The event rate and recruitment progress is assessed in a blinded manner during recruitment before any interim unblinding. If the accumulated blinded data suggests a slower accrual of primary outcome events over calendar time than originally projected, then the number of randomised patients may be increased to a maximum of 4000 patients. Operationally, the recruitment period would be extended and could continue up to 6 months before the target number of events is expected to be achieved. The number of confirmed primary outcome events will not be affected by this consideration and will remain 841 events.

While continuously monitoring the event rate in the above described manner, it is currently planned to include approximately 3600 patients in this trial.

## 10. HISTORY TABLE

Table 10: 1 History table

Version	Date (DD- MMM- YY)	Author	Sections changed	Brief description of change
Final	23-FEB-2017		None	This is the final TSAP without any modification
Revised	11-OCT-2019		4, 6.6.1, 6.8.2, 6.8.3, 7.4.1, 7.4.2, 7.5.1	Exclude FU period from ITT efficacy analyses and add sensitivity analysis including all events for primary endpoint and key secondary endpoint of recurrent HHF.
			4, 7.5.1	Include baseline by time interaction in the slope model
			6.6.2 and 6.8.2	Clarification of time at risk and missing data imputations
			6.7	Add definition of baseline medication
			9.5	Clarification of primary analysis in case of interim stopping
			7.8.1	Changes in the safety analysis strategy in line with empagliflozin strategy (e.g. look specifically into urinary tract malignancy instead of overall malignancy, delete VTE, deleted other significant AEs, update of BICMQ definitions, add hypotension)
			6.1, 7.8.1.6	Add analysis of AEs accounting for treatment switchers
			7.1	Modified focussed baseline presentations (e.g. show HbA1c only for patients with DM, show atrial fibrillation also by AF at baseline, include LVEF , do not include height, LDL, HDL)
			7.2	Modified presentation of medication and non-medication therapy as baseline and separately newly introduced after baseline
			7.5.1	Add individual patient slope and intercept plots by eGFR at baseline.
			7.5.2	Modify renal endpoint as per protocol amendment
			7.6	Add NTproBNP change from baseline by atrial fibrillation or flutter at baseline
			7.6	Add analysis to mean change from baseline after approximately 3 years
			5.3	Add time to investigator reported CV hospitalization
			6.3, 7.6	Add PK set

Table 10: 1 History table (cont.)

Version	Date (DD- MMM- YY)	Author	Sections changed	Brief description of change
			5.4, 6.3, 6.4, 7.6 and where applicable	Clarification of follow-up set, clarification of win ratio to take into account CV death, clarification of definition of atrial fibrillation at baseline vs history of atrial fibrillation, clarification of patient-preferred KCCQ score, other minor clarifications
			6.2 and where applicable	change important protocol “violations” to “deviations” and other minor wording changes.
			Sections 4, 7.4.1, 7.5.1,7.5.2, 7.6, 7.8.2	In all models (e.g., Cox regression, MMRM, et al.) with LVEF included per protocol as a continuous covariate, it has been changed to a categorical variable ( $\leq 30\%$ , $>30\%$ to $\leq 35\%$ , $> 35\%$ ). The reason the change was made was because the inclusion criterion has different NTproBNP thresholds depending on presence or absence of atrial fibrillation and LVEF category. This inclusion criterion stipulates that the relation between LVEF and outcome events is non-monotonic.
			5.3	Definition of CV hospitalisation clarified; Fasting plasma glucose was changed to fasting glucose because it was measured in serum and not plasma
			6.4, 7.8.1	Update of planned subgroup analyses for safety.
			6.4	Based on recommendation from the Executive Steering Committee, the subgroup analyses specified in the TSAP was reduced to the clinically most meaningful ones.
			6.6, 7.5.2	KCCQ-CSS add sensitivity without imputation
			6.6.1	Imputation of missing covariates added.
			6.8.2	Since recurrent event analyses are based on adjudicated event dates and duration of hospital stays is not adjudicated, only the onset dates of the events are considered for the analysis.
			7.4	Specified the primary estimand of the trial
			7.4.2	Clarified definition of investigator reported endpoints, additional sensitivity analysis added
			7.5.1	Joint frailty clarification on analysis details
			7.5.1	Clarify that other secondary endpoints are exploratory

[figure not shown]
Table 10: 1 History table (cont.)

Version	Date (DD- MMM- YY)	Author	Sections changed	Brief description of change
			7.5.1	Multiple imputation for eGFR slope analysis was removed. Under missing at random assumption, the specified multiple imputation approach is asymptotically equivalent to the maximum likelihood estimate and therefore not required in addition.
			7.5.2	Negative binomial regression model for occurrence of all-cause hospitalisation (first and recurrent) added.
			7.5.2, 7.6	Specify MMRM in condensed form (do not include individual terms in case already included as interaction terms with visit or treatment) to be in line with BI internal standards on MMRMs.  Align wording for MMRM term status of diabetes at baseline as well as factors to be included in MMRMs for the other secondary as well as further endpoints.
			7.6	Rules defining ‘win’ and ‘lose’ for the win ratio calculation were modified.
			Section 7.6	Responder analyses (improvement and deterioration of 5 points or more from baseline) for KCCQ clinical summary score, clinical symptoms and physical limitations domain was added.
			9.3	Clarification of diabetes definition
			Throughout and section 9.6	Include wording from the protocol to the TSAP and clarify sample size
Revised	19-NOV-2019		6.2, 6.3	Changes to IPD D2.02 and TS-FU set to reflect change in CTP with regards to open label SGLT-2 inhibitor use after EOT visit
			6.4, 7.6, 10	Typos corrected
Revised	19-JUN-2020		6.8.3, 7.8.1.1	Clarifications with regard to censoring rules
			7.4.2, 7.5.1.1	Addition of sensitivity analyses for COVID-19
			7.8.1.4	Insert word “narrow” for clarification
			9.4, 7.4.4	Add baseline eGFR (5 categories) to subgroups

